#### 5.3 Duration of Therapy

In the absence of treatment delays due to adverse event(s), treatment may continue indefinitely, until one of the following criteria applies:

- Disease progression,
- Intercurrent illness that prevents further administration of treatment,
- Unacceptable adverse event(s),
- Patient decides to withdraw from the study, or
- General or specific changes in the patient's condition render the patient unacceptable for further treatment in the judgment of the investigator.

#### **5.4 Duration of Follow Up**

All patients will be seen at 4 weeks after completion of protocol therapy. Thereafter, continued follow-up is not required for patients who go off protocol treatment with progressive disease, except to document ongoing toxicities (until resolved to < grade 2), late toxicities (including second malignancies) and death. For patients who go off protocol treatment with CR, PR, or SD ongoing, follow-up will be required every 3 months until relapse.

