### 1.2 Secondary Objectives

- To assess time-to progression, median overall survival, and rate of one-year survival in patients with recurrent or metastatic endometrial cancer treated with sunitinib.
- To assess the toxicity associated with sunitinib in patients with recurrent or metastatic endometrial cancer.

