#### 11.1.2 Responsibility for Submissions

Study participants are responsible for submitting CDUS data and/or data forms to the Coordinating Center quarterly by January 31, April 30, July 31, and October 31 to allow time for Coordinating Center compilation, Principal Investigator review, and timely submission to CTEP (see Section 11.1.1.). Please refer to Appendix H, Data

Management Guidelines, for further details regarding data submission requirements.

The Coordinating Center is responsible for compiling and submitting CDUS data to CTEP for all participants and for providing the data to the Principal Investigator for review.

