## Management of Sunitinib-Induced Hypertension\*

## APPENDIX H DATA MANAGEMENT GUIDELINES

### Case Report Form Submission Schedule

Data required for the study will be collected in Case Report Forms provided by the PMH Phase 2 Consortium Central Office. The form submission schedule is outlined below.

Case Report Form	Submission Schedule
Eligibility Checklist	At the time of registration
Baseline Form	Within 3 weeks of on study date
On Treatment Form	Within 3 weeks of the end of each cycle of treatment
Off Treatment Form	Within 3 weeks of the patient coming off-study
Short Follow-up Form	Within 3 weeks of the patient coming to clinic. Required every 3 months until death.
Final Report Form	Within 3 weeks of the patient's death being known to the investigator unless this constitutes a reportable adverse event when it should be reported according to CTEP-AERS guidelines

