### Monitoring

Central data monitoring will take place throughout the trial at the Central Office. On- site monitoring will be performed generally at least once a year at some participating sites.

Once data has been checked and quality assurance performed, it will be entered into an Oracle based relational database by Central Office staff. Further data quality checks will be performed and then the required information will then be submitted to CDUS quarterly.

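### Follow-up stops at relapse in Section 5.4 but runs to death in Appendix H, so survivors' censoring dates for overall survival depend on which text a site follows

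*Combined protocol and SAP*

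**What the plan says.** Section 5.4 has every patient seen 4 weeks after protocol therapy and then splits them by how they stopped.

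- **Stopped in response or stable disease:** "For patients who go off protocol treatment with CR, PR, or SD ongoing, follow-up will be required every 3 months until relapse". Nothing is said about the time after relapse.
- **Stopped with progression:** "continued follow-up is not required for patients who go off protocol treatment with progressive disease, except to document ongoing toxicities", and to document "late toxicities (including second malignancies) and death". No interval is given.

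Appendix H, in its table of case report forms, sets the timing of the Short Follow-up Form: "Within 3 weeks of the patient coming to clinic. Required every 3 months until death". It makes no exception for relapse or progression. The Final Report Form is due within 3 weeks of the patient's "death being known to the investigator unless this constitutes a reportable adverse event". Section 11.1.2 sends sites to Appendix H, the Data "Management Guidelines, for further details regarding data submission requirements".

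The secondary objectives in Section 1.2 include: "To assess time-to progression, median overall survival, and rate of one-year survival". Section 12.1 lists overall survival as a secondary endpoint. Section 12.3 names the Kaplan-Meier method but gives no censoring rule and no common cut-off date.

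**The concern.** For patients who stop in response or stable disease the two schedules conflict: one ends at relapse, the other at death. For patients who stop with progression the texts are unclear rather than flatly contradictory. Section 5.4 waives continued follow-up with exceptions; Appendix H supplies an interval, but times the form from a clinic visit that Section 5.4 does not require after week 4. This second group may be large, since progression is a reason to stop treatment (Section 5.3) and Section 12.1 cites a median progression-free survival of 1.8 to 3.2 months in this setting.

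The Final Report Form does not close the gap. It is triggered by a known death, so it brings deaths up to date and leaves survivors where they were. Kaplan-Meier estimation needs both. If deaths come in and survivors' dates stay at progression, survivors leave the risk set too early and the curve is too low. If enough later deaths are also missed, the curve is too high. Median overall survival and the one-year rate are the estimates at stake.

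**Working it through.** **1. The passages side by side**

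| Patient group | Section 5.4 | Appendix H, Short Follow-up Form |
|---|---|---|
| Stopped in CR, PR or SD, before relapse | every 3 months | every 3 months |
| Same group, after relapse | nothing stated | every 3 months to death |
| Stopped with progression | toxicities and death only, no interval | every 3 months to death, timed from a clinic visit |

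Section 11.1.2 makes Appendix H operative for data submission, but no passage says which text prevails.

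**2. The plan's own figures**

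The plan states no figure for survival or follow-up. Its two-stage response design reproduces: power 0.8649, type I error 0.0582, probability of early stopping 0.4633 and expected sample size 23.05 at a 5% response rate. None of these uses survival.

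**3. Illustration of size: inputs**

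- n = 30 at 2 per month (Section 12.2), so accrual takes 30/2 = 15 months; entry is taken as uniform.
- Assumed median progression-free survival of 3 months, inside the 1.8 to 3.2 months of Section 12.1.
- Assumed median overall survival of 11 months; Table 1 runs from 8.2 to 17.8.
- Assumed data cut, in months after last entry; the documents give none.
- Under Section 5.4 alone, a survivor's last date is progression + 1 month. Otherwise it is the last quarterly contact before the cut.

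Survival is an exponential time to progression plus an exponential residual:

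S(t) = [λ1·exp(−λ2·t) − λ2·exp(−λ1·t)] / (λ1 − λ2)

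Here λ1 = ln 2 / 3 = 0.2310, and λ2 = 0.1092 solves S(11) = 0.5. Then S(12) = (0.2310 × 0.2699 − 0.1092 × 0.0625) / 0.1219 = 0.456, the true one-year survival.

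**4. Results, all deaths captured** (20,000 replicates, Monte Carlo standard error 0.001; mean Kaplan-Meier estimate at 12 months)

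| Cut after last entry | Mean number alive of 30 | 0% under 5.4 alone | 10% | 30% | 50% | 100% |
|---|---|---|---|---|---|---|
| +12 months | 7.1 | 0.452 | 0.445 | 0.429 | 0.413 | 0.365 |
| +24 months | 2.0 | 0.455 | 0.454 | 0.450 | 0.444 | 0.433 |
| +36 months | 0.55 | 0.455 | 0.455 | 0.454 | 0.453 | 0.450 |
| +60 months | 0.04 | 0.455–0.456 throughout | | | | |

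The sampling SD at +12 months is 0.091 to 0.098. The worst cell is 0.365 − 0.456 = −0.091, about one SD. At 10% to 30% the bias is 0.445 − 0.456 = −0.011 to 0.429 − 0.456 = −0.027.

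**5. Direction**

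At +12 months, if only 75%, 50% or 25% of later deaths are captured, the estimate is 0.399, 0.453 or 0.550 with everyone under Section 5.4 alone, and 0.441, 0.454 or 0.469 with 30%.

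**6. Sensitivity to median survival** (100% under Section 5.4 alone, all deaths captured)

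| Median OS | True S(12) | +12 | +24 | +60 |
|---|---|---|---|---|
| 8.2 months | 0.297 | 0.257 | 0.293 | 0.298 |
| 17.8 months | 0.668 | 0.504 | 0.602 | 0.661 |

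The +12-month worst case is therefore 0.257 − 0.297 = −0.04 to 0.504 − 0.668 = −0.16. A separate simulation (3,000 runs) used cuts at +6 and +12 months, progression medians of 1.8 or 3.2 months, and progression and residual medians adding to 8.2, 10.9 or 17.8 months. With all deaths reported and everyone under Section 5.4 alone, it put the estimate 0.11 to 0.24 below complete follow-up.

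**The case against.** The strongest reply is that the two texts govern different things: Section 5.4 governs patient follow-up and Appendix H governs forms. A site that sends the quarterly form satisfies both, and dates go stale only if it ignores a schedule the protocol points it to. Missing forms might also be noticed: "Central data monitoring will take place throughout the trial at the Central Office". That reading is available, and if sites follow it there is almost no bias. But nothing in the protocol states it, and the main body tells the site that routine follow-up has ended.

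Other points on this side stand:

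- The flat conflict covers only patients who stop in response or stable disease and later relapse; the documents give no size for that group. The 100% figures are an upper bound, not the expected effect.
- Capturing every later death while refreshing no survivor is a strained combination. Toxicity follow-up would update some dates, and at 50% capture the errors nearly cancel (0.453 against 0.456).
- The data cut is assumed, and a late one removes the problem.
- Overall survival is descriptive here, and no decision rule uses it.
- A pre-analysis update of vital status is an addition, not a correction of the contradiction.

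These points limit the size and make its sign uncertain. They do not remove the conflict, and the cost of correcting it is very small.

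**Conclusion.** The concern holds. It should be corrected, but it does not threaten the trial's main conclusion. If sites follow Appendix H, or the cut is late (about +36 months or more at a median survival of 11 months), the effect is negligible. At a cut 12 months after last entry with all deaths captured, a 10% to 30% share of patients under Section 5.4 alone lowers one-year survival by about 0.01 to 0.03. The extreme case costs about 0.09, or 0.04 to 0.16 across the medians in Table 1. The sign reverses if enough later deaths go unreported. All of this rests on the assumed data cut, exponential times and censoring dates, so confidence in the size is moderate; the textual conflict itself is certain. The response-rate analysis, the two-stage rule and the prolonged stable disease provision are untouched.

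**What to change.** 1. **Section 5.4 and the Short Follow-up Form row of Appendix H:** state in both that vital status is recorded every 3 months for all patients, including after progression or relapse, until death or data cut-off, and that a telephone or record check is enough when there is no clinic visit.
2. **Section 12.3:** state that vital status is updated for all patients to a common cut-off date before the Kaplan-Meier analysis, and that survivors are censored at the date last known alive.

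The cost is one sentence in Section 5.4, a few words in Appendix H and one sentence in Section 12.3. The added work is a short quarterly check on at most 30 patients, for whom Appendix H already requires a form, plus one update before analysis. No treatment rule changes.

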### **6. DOSING DELAYS/DOSE MODIFICATIONS**

The dose levels and the general approach to dose modification of sunitinib on this trial are shown below. Adverse events (AEs) should be treated with the appropriate maximum supportive care, and dose reductions should be clearly documented in the case report form (CRF). All AEs should be graded according to the Common Terminology Criteria for Adverse Events (CTCAE v3.0).

**Sunitinib dose levels**

Dose Level	Daily Dose
-2	25 mg (one 25 mg capsule)
-1	37.5 mg (one 12.5 capsule plus one 25 mg capsule)
0	50 mg (one 50 mg capsule)

#### **6.1 Management of Treatment-Emergent Hypertension**

Increases in blood pressure (BP) and cases of hypertension have been associated with many drugs acting on the VEGF pathway. The proposed mechanism for this increase is through inhibition of VEGF-induced peripheral vasodilation. Hypertension following sunitinib treatment has rarely been seen in animal studies or clinical trials. Specific guidelines for management of this adverse event and a table of various antihypertensive medications are provided in Appendix F. In addition, guidance on the collection and recording of BP information is provided in Appendix G.

### Management of Hypertension

BP measurements - systolic/diastolic	Treatment/Dose Modification
Patients not receiving maximal antihypertensive therapy:	
≥ 140 mmHg (systolic) OR ≥ 90 mmHg (diastolic)	
 
• Add new or additional antihypertensive meds or increase dose of existing meds
 
• Increase frequency of monitoring until stabilized (e.g., every 48-72 hrs)
 
• Maintain dose of sunitinib
 

≥ 180 mmHg (systolic) OR ≥ 110 mmHg (diastolic) 	
 
• Hold sunitinib
 
• Add new or additional antihypertensive meds or increase dose of existing meds
 
• Monitor patient closely for hypotension (if on antihypertensive meds) until sunitinib is restarted.
 
• Resume treatment at same dose level when BP falls to <140/90.
 

Patients receiving maximal antihypertensive therapy  (four antihypertensives for 2 weeks without dose modification of antihypertensive medications): diuretics, beta blocker or central sympathetic blocker, ACE inhibitor or ARB and vasodilator or calcium channel blocker (CCB)	

 
• 160 mmHg (systolic) OR ≥ 105 mmHg (diastolic)
 
	
 
• Hold sunitinib
 
• Maintain antihypertensive meds and monitor patient closely for hypotension until sunitinib is restarted.
 
• Resume treatment at one lower dose level when BP falls to <140/90
 

 
1. Any patient with symptomatic severe hypertension (i.e., ≥ 180 / 110) should have sunitinib stopped and treatment initiated as per hypertensive crisis (e.g., hospitalization, monitoring, IV therapy)
 
2. Maximal antihypertensive therapy is defined as four antihypertensive medications given for 2 weeks.
 
3. If hypertension persists despite two dose level reductions, sunitinib must be discontinued.
 
	

- While patients are receiving treatment with sunitinib, the early initiation of antihypertensive treatment for grade 1 or 2 hypertension to minimize more severe or persistent hypertension is not considered a grade 3 adverse event.
- Decisions to hold or decrease the sunitinib dose during treatment must be based on BP readings taken in the clinic by a medical professional.

#### 6.2 Left ventricular systolic dysfunction / CHF

- **Symptomatic Cardiac Events**

Discontinue sunitinib if:

- a patient has symptoms of CHF and a diagnosis of CHF is confirmed

- a patient has a myocardial infarction
- **Asymptomatic Decrease in LVEF**  
(Applicable only to patients undergoing routine cardiac monitoring as outlined in Section 5.1)

The decision to continue or hold sunitinib is based on the ejection fraction as it relates to the institution's LLN **and** change in ejection fraction from screening (LVEF as measured at registration) according to the following table:

Relationship of LVEF to institution's LLN	Decrease < 10%	Decrease 10-15%	Decrease $\geq 16\%$
Normal	Continue	Continue	Continue Repeat MUGA / ECHO in 6 weeks
1-5% below LLN	Continue Repeat MUGA / ECHO in 6 weeks	Continue Repeat MUGA / ECHO in 6 weeks	HOLD Repeat MUGA / ECHO in 6 weeks
$\geq 6\%$ below LLN	Continue Repeat MUGA / ECHO in 6 weeks	HOLD Repeat MUGA / ECHO in 6 weeks	HOLD Repeat MUGA / ECHO in 6 weeks

Discontinue sunitinib if:

- Two consecutive HOLD categories occur
- Three intermittent HOLD categories occur. (At the discretion of the investigator, sunitinib may also be permanently discontinued prior to the occurrence of 3 intermittent HOLD categories)

IF LVEF is maintained at a "Continue" or improves from a "HOLD" to a "Continue" category, additional MUGA scans / echocardiograms prior to the next scheduled MUGA / echo will be at the discretion of the investigator, as clinically indicated.

### 6.3 Other Hematologic and Non-Hematologic Adverse Events

Event	AE Grade or Observation	Dose modification
Neutropenia	Grades 1 and 2	Maintain dose
	Grade 3 *	Hold sunitinib until $\leq$ grade 2, then resume at same dose level
	Grade 4	Hold sunitinib until $\leq$ grade 2, then reduce 1 dose level and resume treatment
Thrombocytopenia	Grades 1 and 2	Maintain dose
	Grade 3 *	Hold sunitinib until $\leq$ grade 2, then resume at same dose level
	Grade 4	Hold sunitinib until $\leq$ grade 2, then reduce 1 dose level and resume treatment
Fatigue (lethargy, malaise, asthenia)	Grades 1 and 2	Maintain dose
	Grade 3 *	Hold sunitinib until $\leq$ grade 2, then reduce 1 dose level and resume treatment
	Grade 4	Hold sunitinib until $\leq$ grade 2, then reduce 1 dose level and resume treatment
QTc Prolongation	>450 but $<$ 550 msec	
 
Review patient's concomitant medications for QT interval-prolonging agents. Correct any electrolyte abnormalities.
 
Continue sunitinib at current dose level.
 

	$\geq$ 550 msec	
 
Stop sunitinib and any other QT-interval prolonging agents immediately. Correct any electrolyte abnormalities, then                     
 
If there is a plausible explanation for AE other than sunitinib treatment, resume sunitinib at current dose level.
 
If sunitinib may have contributed to the AE:                             
 
Reduce 2 dose levels and restart sunitinib.
 
If QTc remains <math><500</math> msec after 14 days at reduced dose, increase one dose level and continue sunitinib.
 
 
 
 
 
 
If QTc remains <math><500</math> msec after 14 days, original dose of sunitinib may be resumed.

Hand-foot syndrome	Grades 1 and 2	Maintain dose
	Grade 3	Hold sunitinib until $\leq$ grade 1, then reduce 1 dose level
	Grade 4	Discontinue treatment
Serum lipase /	Grades 1 and	Maintain dose

amylase	2	
	Grades 3 and 4	Hold sunitinib until $\leq$ grade 1, then reduce 1 dose level
ALT / AST / Bilirubin	$\geq$ Grade 3	Sunitinib should be dose delayed, may be re-administered when levels of ALT / AST / bilirubin is $\leq$ grade 2. Sunitinib should NOT be re-administered if subjects develop $\geq$ grade 3 hepatic failure (CTCAEv4 definition).

- **Recurrent grade 3 events require dose reduction.**

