## 3.2 Exclusion Criteria

3.2.1 Patients who have had chemotherapy or radiotherapy within 4 weeks (6 weeks for nitrosoureas or mitomycin C) prior to entering the study or those who have not recovered from adverse events due to agents administered more than 4 weeks earlier. At least 4 weeks must have elapsed since any major surgery.

3.2.2 Patients may not be receiving any other investigational agents.

3.2.3 Patients who have received prior treatment with any other antiangiogenic agent (*e.g.*, bevacizumab, sorafenib, pazopanib, AZD2171, PTK787, VEGF Trap, etc.) are ineligible.

3.2.4 History of allergic reactions attributed to compounds of similar chemical or biologic composition to sunitinib.

3.2.5 Patients who have a history of serious ventricular arrhythmias (VT or VF equal to or greater than 3 beats in a row), QTc prolongation (defined as a QTc interval equal to or greater than 500 msec) or other significant ECG abnormalities are excluded.

3.2.6 Patients with poorly controlled hypertension (systolic blood pressure of 140 mmHg or higher or diastolic blood pressure of 90 mmHg or higher) are ineligible.

3.2.7 Patients who require use of therapeutic doses of coumarin-derivative anticoagulants such as warfarin are excluded, although doses of up to 2 mg daily are permitted for prophylaxis of thrombosis. Note: Low molecular weight heparin is permitted provided the patient's PT INR is  $\leq 1.5$ .

3.2.8 Patients with any condition (*e.g.*, gastrointestinal tract disease resulting in an inability to take oral medication or a requirement for IV alimentation, prior surgical procedures affecting absorption, or active peptic ulcer disease) that impairs their ability to swallow and retain sunitinib tablets are excluded.

3.2.9 Patients with any of the following conditions are excluded:

- Serious or non-healing wound, ulcer, or bone fracture.
- History of abdominal fistula, gastrointestinal perforation, or intra-abdominal abscess within 28 days of treatment.
- Any history of cerebrovascular accident (CVA) or transient ischemic attack within 12 months prior to study entry.
- History of myocardial infarction, cardiac arrhythmia, stable/unstable angina, symptomatic congestive heart failure, or coronary/peripheral artery bypass graft or stenting within 12 months prior to study entry.
- History of pulmonary embolism within the past 12 months.
- Class III or IV heart failure as defined by the NYHA functional classification system (see Appendix B).

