		Eye disorders - Other (vision deterioration)	Eye disorders - Other (vision deterioration) (Gr 2)
	Papilledema		Papilledema (Gr 2)
GASTROINTESTINAL DISORDERS			
	Abdominal distension		Abdominal distension (Gr 2)
Abdominal pain			Abdominal pain (Gr 3)
Anal mucositis			Anal mucositis (Gr 2)
Constipation			Constipation (Gr 2)
Diarrhea			Diarrhea (Gr 3)
	Dry mouth		Dry mouth (Gr 2)
Dyspepsia			Dyspepsia (Gr 2)
		Esophagitis	
	Flatulence		Flatulence (Gr 2)
	Gastritis		Gastritis (Gr 2)
	Gastroesophageal reflux disease		
		Gastrointestinal perforation 	
Mucositis oral			Mucositis oral (Gr 3)
Nausea			Nausea (Gr 3)
	Oral pain		Oral pain (Gr 2)
		Pancreatitis	
Rectal mucositis			Rectal mucositis (Gr 2)
Small intestinal mucositis			Small intestinal mucositis (Gr 2)
Vomiting			Vomiting (Gr 3)
GENERAL DISORDERS AND ADMINISTRATION SITE CONDITIONS			
	Chills		Chills (Gr 2)
	Edema limbs		Edema limbs (Gr 2)
Fatigue			Fatigue (Gr 3)
	Fever		Fever (Gr 2)
	Non-cardiac chest pain		Non-cardiac chest pain (Gr 2)
HEPATOBILIARY DISORDERS			
		Cholecystitis	
		Hepatic failure	
IMMUNE SYSTEM DISORDERS			
		Allergic reaction 	
INFECTIONS AND INFESTATIONS			
		Infection and infestations - Other (necrotizing fasciitis)	
INJURY, POISONING AND PROCEDURAL COMPLICATIONS			
		Wound complication	
INVESTIGATIONS			
	Alanine aminotransferase increased		Alanine aminotransferase increased (Gr 3)
	Alkaline phosphatase increased		Alkaline phosphatase increased (Gr 2)
	Aspartate aminotransferase increased		Aspartate aminotransferase increased (Gr 3)
	Blood bilirubin increased		Blood bilirubin increased (Gr 2)
	CPK increased		

Adverse Events with Possible Relationship to Sunitinib malate (SU011248 L-malate) (CTCAE 4.0 Term) [n= 7115]			Specific Protocol Exceptions to Expedited Reporting (SPEER)
Likely (>20%)	Less Likely (<=20%)	Rare but Serious (<3%)	
	Creatinine increased		Creatinine increased (Gr 3)
		Electrocardiogram QT corrected interval prolonged	
	Lipase increased		Lipase increased (Gr 4)
	Lymphocyte count decreased		Lymphocyte count decreased (Gr 2)
	Neutrophil count decreased		Neutrophil count decreased (Gr 4)
	Platelet count decreased		Platelet count decreased (Gr 4)

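### After a stop for QTc of 550 msec or more, section 6.3 states no QTc condition for restart, and its two restart branches can overlap or point below the dose table

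*Combined protocol and SAP*

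**What the plan says.** The QTc entry in the section 6.3 table has two rows. Above 450 and below 550 msec, sunitinib continues at the current dose while co-medication and electrolytes are reviewed. At 550 msec or more the instruction is: "Stop sunitinib and any other QT-interval prolonging agents immediately. Correct any electrolyte abnormalities, then" one of two branches.

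- Branch 1: "If there is a plausible explanation for AE other than sunitinib treatment, resume sunitinib at current dose level".
- Branch 2: "If sunitinib may have contributed to the AE", the action is "Reduce 2 dose levels and restart sunitinib". If QTc stays under 500 msec for 14 days, the dose goes up one level, and a further sentence allows return to the original dose on the same QTc condition after 14 days.

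The dose levels at the start of section 6 are 0 (50 mg), -1 (37.5 mg) and -2 (25 mg). Nothing lower is listed.

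Appendix J prohibits a list of QT-prolonging drugs during the study and allows sunitinib after a washout of about five half-lives. The study calendar requires an ECG at baseline and leaves later ECGs to clinical indication.

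**The concern.** The row tells the site when to stop and what dose to give on return, but not what the QTc must be at that point. The only step between stop and restart is "Correct any electrolyte abnormalities, then". If a patient's electrolytes were never abnormal, that step is already complete.

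The two branch conditions are also not opposites. A co-medication or a low potassium can be a plausible explanation while sunitinib may also have played a part, and the row gives no order of precedence.

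This is a multicentre protocol. Two sites applying the row in good faith to the same event could restart at different QTc values and at different doses. A site with a patient who has already been reduced may find no listed dose to apply. The consequences are for patient safety and for consistent dosing. No sample size, error rate or endpoint definition is affected.

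**Working it through.** No formula or stated figure in the plan applies here. The check sets the passages side by side and does the dose-level arithmetic.

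**Step 1. How the hold is lifted in each event group of section 6.3**

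| Event group | Condition before sunitinib is resumed |
|---|---|
| Neutropenia | grade 2 or lower |
| Thrombocytopenia | grade 2 or lower |
| Fatigue | grade 2 or lower |
| Hand-foot syndrome (grade 3) | grade 1 or lower |
| Lipase / amylase | grade 1 or lower |
| ALT / AST / bilirubin | grade 2 or lower |
| QTc of 550 msec or more | electrolytes corrected; no QTc value |

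Six of the seven groups have a recovery condition tied to the event itself, and QTc does not. Hypertension in section 6.1 also has one (below 140/90).

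**Step 2. Whether another section supplies the condition**

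- Section 6.4 is limited by its heading to events that the preceding sections do not cover. Its general two-week limit on holds caps time off drug and sets no QTc.
- The calendar fixes no ECG after baseline.
- Appendix J sets an interval (for example 5 days for haloperidol or flecainide), but only where a listed drug was used. It gives no QTc value.

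**Step 3. What the row's own figures imply**

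- The lower row continues sunitinib below 550 msec, which suggests restart is acceptable under 550.
- The re-escalation step in branch 2 asks whether QTc *remains* under 500 msec, which presupposes it was under 500 at restart.
- The two readings differ for any QTc from 500 up to, but not including, 550 msec. Branch 1 has no 500 msec wording of its own.
- At 550 msec or more, with electrolytes corrected, a patient meets a restart branch and also "Stop sunitinib and any other QT-interval prolonging agents immediately". The row is circular there.

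**Step 4. Restart dose by branch**

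Branch 1 keeps the current level. Branch 2 is the current level minus 2.

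| Level at event | Branch 1 | Branch 2 |
|---|---|---|
| 0 (50 mg) | 50 mg | 0 - 2 = -2, 25 mg |
| -1 (37.5 mg) | 37.5 mg | -1 - 2 = -3, not listed |
| -2 (25 mg) | 25 mg | -2 - 2 = -4, not listed |

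At level 0 the branches differ by a factor of 50 / 25 = 2, and under branch 2 the lower dose lasts at least 14 days. From either reduced level, branch 2 points outside the dose table.

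**The case against.** The best reply is that the row, read as a whole, contains its own bound. Dosing at 550 msec or more would break the stop instruction, so nobody should infer permission to do it. Branch 2's wording presupposes a value under 500. Where another drug is the cause, Appendix J imposes an interval; where electrolytes are the cause, they must be corrected first. The two branches can also be read as an ordinary attribution split: section 7.2 defines a possible relationship as one that may exist, so a single attribution per event would select a single branch.

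Much of this stands, and it rules out several stronger readings that a reader might draw:

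- *That the protocol authorises restart at any QTc, without upper bound.* It does not. It gives conflicting instructions at 550 msec or more and leaves the condition to inference below that.
- *That patients are always restarted at once.* Appendix J delays sunitinib when a listed drug was involved.
- *That the row contradicts the entry criteria.* Section 3.2.5 excludes "QTc prolongation (defined as a QTc interval equal to or greater than 500 msec"), and 3.1.9 requires a value below 500. These govern entry; section 6.3 openly uses a different limit on treatment.
- *That listing "Electrocardiogram QT corrected interval prolonged" in section 7.1 proves the branches overlap.* That table describes the agent's risks. It does not decide causality for a given patient.

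What the reply does not remove: the two implied values disagree, Appendix J is silent when no listed drug was used, and the row does not refer to the attribution scale in 7.2. Even with that scale, a site can judge another cause plausible and sunitinib's contribution possible in the same patient.

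**Conclusion.** The point holds as a defect of wording in a safety instruction. The restart is unspecified for QTc and circular at 550 msec or more. The branches are not mutually exclusive. The two-level reduction has no listed dose from two of the three dose levels. The contrast of 50 mg with 25 mg applies only to a patient at level 0 who meets both conditions.

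The overlap finding assumes that the branch conditions are read in their ordinary sense, without importing the 7.2 scale. The circularity finding assumes that the row is followed literally.

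How often this would arise cannot be derived from the documents. Section 7.1 places QTc prolongation in a column headed below 3%; for 30 patients that is fewer than 30 x 0.03 = 0.9, but it is not a rate for 550 msec or more in this population. The case for correction rests on the seriousness of the event and the low cost of the change, not on expected numbers.

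**What to change.** The sponsor's clinicians should reconcile the restart wording in the upper QTc row of section 6.3 with:

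- the row's own stop trigger;
- the 500 and 550 msec figures in the two QTc rows;
- the washout provision in Appendix J;
- the dose-level table in section 6, for patients already at level -1 or -2.

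They should also reword the two branches so that each patient falls in only one. If the attribution scale in section 7.2 is meant to decide between them, the row should say so. Which QTc value, dose or restart rule applies is theirs to settle, and none is proposed here.

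The cost is a few sentences in one table row. Design, sample size, endpoints and analysis are unchanged.
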